#### **4.4 END OF STUDY DEFINITION**

Please refer to the master protocol.

## 5 STUDY POPULATION

See the master protocol for a full list of common inclusion and exclusion criteria and the subsections below for Cohort A1-specific criteria.

### 5.1 INCLUSION CRITERIA

Participants are eligible to be included in the study only if all of the following criteria apply (in addition to the criteria listed in the master protocol):

#### Type of participant and disease characteristics

- I 01. PD-L1 expression CPS as determined preferably using a locally approved assay (with an absolute value provided to Sponsor) at local laboratory (for details on PD-L1 assay, please refer to lab manual)
- PD-L1 expression CPS  $\geq 1$  (with an absolute value provided to Sponsor).
- I 02. Provision of tumor tissue:
- **Mandatory baseline biopsy in Core Phase** (minimum 5 slides with 4-5 micron thickness for the first 20 participants who have signed ICF, excluding screening failure participants, minimum 10 slides with 4-5 micron thickness for subsequent participants). Archival tumor tissue samples should be obtained from biopsies done within 6 months, and there should be no systemic anti-cancer therapy between collection of biopsy and enrollment. Slides specifications are detailed in Lab Manual.
  - The Sponsor may approve the written request to enroll, on a case-by-case basis, participants with:
    - location of the tumor not amenable to biopsy due to significant risk, OR
    - less than required number of slides or archival tumor tissue sample collected more than 6 months prior to enrollment.
- I 03. Prior anticancer therapy
- Have not received prior systemic therapy for **R/M disease**. Participants who received systemic therapy as part of multimodal treatment for locally advanced disease are eligible if the systemic therapy was completed at least 6 months prior to enrollment.

### 5.2 EXCLUSION CRITERIA

Participants are excluded from the study if any of the following criteria apply (in addition to the criteria listed in the master protocol):

#### Prior/concomitant therapy

- E 01. Prior treatment with an agent (approved or investigational) that blocks the PD-1/PD-L1 pathway (participants who joined a study with an anti-PD-1/PD-L1 in the experimental arm but have written confirmation they have not received anti-PD-1/PD-L1 are allowed).

### **5.3 LIFESTYLE CONSIDERATIONS**

Please refer to the master protocol.

### **5.4 SCREEN FAILURES**

Please refer to the master protocol.

### **5.5 CRITERIA FOR TEMPORARILY DELAYING [ENROLLMENT/RANDOMIZATION/ADMINISTRATION OF STUDY INTERVENTION ADMINISTRATION]**

Please refer to the master protocol.

## 6 STUDY INTERVENTION(S) AND CONCOMITANT THERAPY

### 6.1 STUDY INTERVENTION(S) ADMINISTERED

Please refer to the master protocol.

The maximum number of cycles allowed in this Cohort A1 substudy is 35 cycles.

Dosing sequence: [REDACTED]

#### 6.1.1 Investigational medicinal product

Investigational medicinal product (IMP) is defined as SAR444245, and pembrolizumab administered as described in Section 4.1. Details of each IMP component to be administered are shown in Table 1.

Preparation and administration of IMP are detailed in the pharmacy manual. Hydration is required for SAR444245 infusions. Details are provided in Section 6.1.3 of the master protocol.

**Table 1 - Overview of IMP administered**

| Intervention name                   | SAR444245           | Pembrolizumab  |
|-------------------------------------|---------------------|--|
| Type                                | See master protocol | Biologic   |
| Dose formulation                    | See master protocol | Solution for infusion  |
| Unit dose strength(s)               | See master protocol | 25 mg/mL   |
| Dosage level(s) a        | 24 µg/kg Q3W        | 200 mg Q3W   |
| Route of administration             | See master protocol | IV infusion  |
| Use                                 | See master protocol | Treatment of cancer (combination)  |
| IMP or NIMP                         | IMP                 | IMP  |
| Packaging and labeling              | See master protocol | Supplied in single-dose vials containing 100 mg/4 mL pembrolizumab labelled with a multilingual booklet. 1 vial per treatment box. |
| Current/Former name(s) or alias(es) | NA                  | Keytruda   |

a The total dose will be calculated based on the weight on the day of the infusion or the most recent weight assuming it was assessed in a reasonable time frame according to Investigator assessment. Study sites should make every effort to measure body weight as close to the infusion day as possible considering the variability of local process from site to site. If the infusion is prepared with the most recent weight assessed in a reasonable time frame, the participant must still be weighed on D1 of each cycle, and the weight recorded in the electronic case report form (e-CRF). Study sites should make every effort to target infusion timing to be as close to 30 minutes as possible. However, given the variability of infusion pumps from site to site, a window between -5 minutes and +10 minutes is permitted (ie, infusion time is 30 minutes -5 min/+10 min).

### **6.1.2 Non-investigational medicinal product**

Please refer to the master protocol.

### **6.1.3 Hydration guidelines for SAR444245 administration**

Please refer to the master protocol.

### **6.1.4 Readiness for treatment of severe cytokine release syndrome**

Please refer to the master protocol.

## **6.2 PREPARATION/HANDLING/STORAGE/ACCOUNTABILITY**

Please refer to the master protocol.

## **6.3 MEASURES TO MINIMIZE BIAS: RANDOMIZATION AND BLINDING**

Not applicable.

## **6.4 STUDY INTERVENTION COMPLIANCE**

Please refer to the master protocol.

## **6.5 DOSE MODIFICATION**

### **6.5.1 General rules**

Dose modifications for SAR444245 is permitted according to the guidelines described in this section. Pembrolizumab dose reductions are not permitted. Pembrolizumab treatment may be interrupted or discontinued due to toxicity.

Dose modifications different from those stated in the protocol should only be made in consultation with the Sponsor, unless required for immediate participant safety.

**Cycle delay** (ie, Day 1 should be delayed for all IMPs) is permitted in case of treatment-emergent adverse event (TEAE). Dose modification will be made according to the worst grade of toxicity observed within a cycle. If a participant experiences several toxicities and there are conflicting recommendations, the most conservative recommended dose adjustment should be followed. Once a dose has been decreased, intra-patient re-escalation back to the previous dose level is not permitted.

Administration of the study treatment will be discontinued in the event of a TEAE that persists despite appropriate dose modifications or any other TEAE that, in the opinion of the Investigator, warrants discontinuation.

If any of the IMP components is permanently discontinued, the other IMP component can be continued until disease progression or other criteria as detailed in Section 7.1.1 of the master protocol are met. In this case, it is partial permanent discontinuation, and the end of treatment (EOT) assessment will be 30 days after the date of the last administration of the remaining IMP. When all IMP components are permanently discontinued, it is full permanent discontinuation.

All changes to study treatment administration must be recorded in the electronic case report form (e-CRF).

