### 6.5.2 Cycle delay

The treatment window is  $\pm 3$  days for each of the Q3W administrations. A cycle is deemed to have been delayed if the treatment is administered  $\geq 4$  days beyond the theoretical day of Q3W IMP administration. The participant may receive the next dose after recovery from the toxicity as described in Section 6.5.3. After cycle delayed, such participants may be considered for treatment resumption once the toxicity resolves or improves to Grade 1 or baseline.

Participants may have cycle delay, if toxicity occurs and the participant does not recover according to following rules:

- For Q3W IMP administration: If toxicity occurs and the participant does not recover on the day of planned administration, the cycle will be delayed; restart of study IMPs could occur only on the initiation of the subsequent cycle.
- In case of cycle delay for the recovery of toxicity, the following rules should be followed for restart or discontinuation of the treatment:
  - In case of a cycle delay up to 14 days, it is per Investigator's decision to restart the study treatment.
  - After a cycle delay of  $>14$  days and  $\leq 84$  days, it is per Investigator's decision to restart the study treatment, if a clear benefit from treatment is observed and after consultation with the Sponsor.
  - The study treatment must be permanently discontinued if the cycle delay is longer than 84 days.
- Cycle may be delayed for situations other than TEAEs such as medical/surgical events or logistical reasons not related to study therapy. Participants should be placed back on study therapy within 21 days of the scheduled delay, unless otherwise discussed with the Sponsor (for example for national or regional emergencies). The reason for this delay should be documented in the participant's study record.

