### 6.5.3 General guidelines for the management of treatment-related adverse events

Participants who experience Grade  $\geq 3$  TRAEs at any time of the study (including clinically significant Grade 3 laboratory abnormalities as defined in Section 10.3.1 of the master protocol) will be required to temporarily cycle delay the IMP, unless specified otherwise in the protocol, and with the exception of the TRAEs resolving within 5 days. After cycle delay, such participants may be considered for treatment resumption once the TRAE resolves or improves to Grade 1 or baseline. Treatment resumption is at the discretion of the Investigator and Sponsor, if thought to be in the best interest of the participant, except when specified otherwise in this protocol, or if the event has required the IMP temporary interruption for more than 84 days from the last scheduled dose.

The cycle delay of treatment for Grade 2 events is left at the discretion of the Investigator unless otherwise specified in this protocol.

No cycle delay of treatment or dose modification is required for Grade 1 events.

Dose reduction for SAR444245 from  $\blacksquare \mu\text{g}/\text{kg}$  to  $\blacksquare \mu\text{g}/\text{kg}$  or another lower dose may be decided when specified in the protocol or following discussions with the Sponsor.

The final decision on dose modification and/or corrective therapy will be based on the Investigator's judgment, in the best interest of the participant.

Recommended guidelines for the management of specific AEs including irAE, CRS, Vascular Leak Syndrome (VLS) and IRRs are presented in [Section 6.5.4](#).

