| 
Grade 3
 
 
• Feverb (Temperature <math>\geq 38^{\circ}\text{C}</math>)
 
• Hypotension requiring a vasopressor with or without vasopressin
 
• And/orc hypoxia requiring high-flow nasal cannulad, face mask, nonrebreather mask, or Venturi mask
 
  | 
If CRS grade 3, temporarily cycle delay SAR444245, and resume subsequent treatment only when symptoms have resolved or improved to Grade 1.
 
SAR444245 can be either restarted at ■ <math>\mu\text{g}/\text{kg}</math> or permanently discontinued, as clinically indicated.
  |
| 
Grade 4
 
Life-threatening consequences; urgent intervention indicated
 
 
• Feverb (Temperature <math>\geq 38^{\circ}\text{C}</math>)
 
• Hypotension requiring multiple vasopressors (excluding vasopressin)
 
• And/orc hypoxia requiring positive pressure (eg, CPAP, BiPAP, intubation and mechanical ventilation)
 
 | 
If CRS Grade 4, permanently discontinue SAR444245.
 
If CRS Grade 3 or Grade 4, initiate IV corticosteroids (outside of the context of CAR-T cells, corticosteroids alone maybe initiated in first intention) and tocilizumab or alternative therapies per site practice in CRS management considered, and/or epinephrine and/or other vasopressors should be administered as needed. Participants with severe CRS may require management in intensive care setting, with monitoring of clinical status and laboratory tests performed at least daily.
 
As the participant improves, the intensity of the monitoring and setting can be decreased, but the participant should not be discharged from the hospital until clinically stable. Corticosteroids can then be administered IV or orally every 8 hours for up to 3 days, then tapered over 4 days. In
   |

| Event severity (ASTCT CRS Consensus Grading) | Recommended SAR444245 dose modification and supportive care guidelines  |
|--|---|
|  | 
general, tapering of steroids can start when vasopressors and high-flow oxygen are no longer needed.
 
CRS is considered resolved when there is sustained resolution of fever and there is no longer a need for oxygen supplementation to relieve hypoxia nor vasopressors to maintain blood pressure; however, normalization of temperature alone does not define resolution of CRS.
   |

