a SAR444245 to be withheld plus pembrolizumab to be withheld corresponds to "cycle delay".

b Permanently discontinuation of full study treatment.

c AST/ALT: >3.0 to 5.0 x ULN if baseline normal; >3.0 to 5.0 x baseline, if baseline abnormal; bilirubin:>1.5 to 3.0 x ULN if baseline normal; >1.5 to 3.0 x baseline if baseline abnormal.

d AST/ALT: >5.0 to 20.0 x ULN, if baseline normal; >5.0 to 20.0 x baseline, if baseline abnormal; bilirubin:>3.0 to 10.0 x ULN if baseline normal; >3.0 to 10.0 x baseline if baseline abnormal.

e AST/ALT: >20.0 x ULN, if baseline normal; >20.0 x baseline, if baseline abnormal; bilirubin: >10.0 x ULN if baseline normal; >10.0 x baseline if baseline abnormal.

f The decision to withhold or permanently discontinue pembrolizumab and SAR444245 is at the discretion of the investigator or treating physician. If control achieved or ≤Grade 2, pembrolizumab and SAR444245 may be resumed.

g Events that require discontinuation include but are not limited to: encephalitis and other clinically important irAEs (eg. vasculitis and sclerosing cholangitis).

AE(s)=adverse event(s); ALT= alanine aminotransferase; AST=aspartate aminotransferase; CTCAE=Common Terminology Criteria for Adverse Events; DRESS=Drug Rash with Eosinophilia and Systemic Symptom; GI=gastrointestinal; IO=immuno-oncology; ir=immune related; IV=intravenous; SJS=Stevens-Johnson Syndrome; T1DM=type 1 diabetes mellitus; TEN=Toxic Epidermal Necrolysis; ULN=upper limit of normal.

Note: Non-irAE will be managed as appropriate, following clinical practice recommendations.

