| Severe or Life-threatening
Grade 3
ICE score 0-2. Awakens only to tactile stimulus.
Any clinical seizure focal or generalized that resolves rapidly or nonconvulsive seizures on EEG that resolve with intervention.
Grade 4
ICE score: 0 (participant is unarousable and unable to perform ICE).
Participant is unarousable or requires vigorous or repetitive tactile stimuli to arouse. Stupor or coma.
Life-threatening prolonged seizure (>5 min); or Repetitive clinical or electrical seizures without return to baseline in between.
Deep focal motor weakness such as hemiparesis or paraparesis.
Diffuse cerebral edema on neuroimaging; decerebrate or decorticate posturing; or cranial nerve VI palsy; or papilledema; or Cushing's triad. | If Grade 3 ICANS, delay SAR444245.
When symptoms have resolved or improved to Grade 1 after corticosteroid taper, SAR444245 can be either restarted at ■ μg/kg or permanently discontinued, as clinically indicated, and upon discussions between the Investigator and Sponsor.
Treatment with IV corticosteroids should be initiated. Concomitant CRS may require tocilizumab or alternative therapies per site practice in CRS management and should be handled as described in Section 6.5.4.3.
Corticosteroids can then be administered IV or orally every 8 hours for up to 3 days, then tapered over 4 days.

If Grade 4 ICANS, permanently discontinue SAR444245.
Treatment with IV corticosteroids should be initiated. Concomitant CRS may require tocilizumab or alternative therapies per site practice in CRS management and should be handled as described in Section 6.5.4.3.
Corticosteroids can then be administered IV or orally every 8 hours for up to 3 days, then tapered over 4 days.

For both Grade 3 and Grade 4 ICANS
If there is no clinical improvement within 24 to 72 hours, then re-evaluation for other contributing conditions should be done. Administration of IV Tocilizumab at 8 mg/kg (for participants weighing ≥30 kg, total dose should not exceed 800 mg) or alternative therapies per site practice in CRS management should be considered, and steroids should be administered concurrently and repeated as previously mentioned for CRS. Neurologist and other relevant clinical specialists should be involved whenever indicated. |

a Information for preparation and storage of SAR444245 is provided in the pharmacy manual  

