**Table 7 - Guidelines for the management of Vascular Leak Syndrome (VLS)**

| Event severity
(NCI-CTCAE V5.0)   | Recommended SAR444245
dose modification and supportive care guidelines  |
|--|--|
| Mild
Grade 1
Asymptomatic   | No intervention required other than clinical monitoring.  |
| Moderate
Grade 2
Symptomatic; medical intervention indicated  | Delay SAR444245. Upon resolution of VLS or improvement to Grade 1, SAR444245a can be resumed at the reduced dose of █ μg/kg.
The initial strategy is to administer boluses of crystalloids with a goal of providing the minimum effective volume that optimizes blood pressure together with a fluid-restrictive strategy is advocated to limit interstitial fluid volume expansion.  |
| Severe or Life-threatening
Grade 3:
Severe symptoms; intervention indicated

Grade 4:
Life-threatening consequences; urgent intervention indicated | If Grade 3 or Grade 4 VLS, permanently discontinue SAR444245.
In participants with severe shock, blood pressure may be only partially responsive or refractory to IV crystalloid fluids.
Severe or persistent hypotension is to be managed by the administration of vasopressors. A trial of 25% albumin IV is an additional option, although its efficacy is limited to those with a severe capillary leak. In those who remain with refractory shock in the setting of low filling pressures, high molecular weight starches such as hetastarch (MW 450 kDa) and pentastarch (MW 264 kDa) may be effective in expanding the intravascular volume. Supportive care with invasive and noninvasive ventilation as well as renal replacement may be necessary in severe cases. When available, disease-specific therapy should be initiated as soon as possible to facilitate recovery. |
|  | During the recovery phase from severe capillary leak, the endothelial injury resolves and the capillary leak becomes less important, resulting in stabilization of blood pressure, at which time fluid overload symptoms and signs may predominate (eg, pulmonary edema, pleural effusions, acute respiratory distress syndrome, systemic edema, ascites). Volume removal with loop diuretics is the first-line therapy in these patients. In those with   |

| Event severity
(NCI-CTCAE V5.0) | Recommended SAR444245
dose modification and supportive care guidelines   |
|--|---|

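### Substudy 01 defines a cycle delay as holding both drugs, but the CRS Grade 3 row applies the term to SAR444245 alone, and the ICANS and VLS delay rows leave pembrolizumab unaddressed

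*Protocol*

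**What the plan says.** All references are to Substudy 01 (Cohort A1) unless stated.

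**General rules**
- Section 6.1.1 covers both drugs: "Investigational medicinal product (IMP) is defined as SAR444245, and pembrolizumab administered as described in Section 4.1".
- Section 6.5.1 glosses a cycle delay as "Day 1 should be delayed for all IMPs".
- Section 6.5.2 says of a participant who has not recovered on the planned day that "restart of study IMPs could occur only on the initiation of the subsequent cycle".
- Section 6.5.3 says that participants with Grade 3 or higher treatment-related events "will be required to temporarily cycle delay the IMP, unless specified otherwise in the protocol". Events that resolve within 5 days are exempt.
- Table 5, footnote a, says that "SAR444245 to be withheld plus pembrolizumab to be withheld corresponds to" a cycle delay.

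**Event-specific rows**
- Table 4, CRS Grade 3: "temporarily cycle delay SAR444245".
- Table 6, ICANS Grade 3: "If Grade 3 ICANS, delay SAR444245". The Grade 2 row also delays SAR444245.
- Table 7, VLS Grade 2: "Delay SAR444245. Upon resolution of VLS or improvement to Grade 1".

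The guidance columns of these three tables are headed as guidance for SAR444245. None of the delay rows says what happens to pembrolizumab.

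**The concern.** Cycle delay is a working term with one stated meaning: the whole cycle moves and both drugs move with it. When an event table uses that term for one named drug, a site can read it in two ways. Either the cycle is delayed as defined and pembrolizumab waits too, or the table is a drug-specific instruction and pembrolizumab is given on its planned day. The documents do not say which.

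At stake is whether pembrolizumab is given while a Grade 3 CRS, a Grade 2 or 3 ICANS or a Grade 2 VLS is unresolved, and whether such a dose counts as a cycle. Cycle numbering matters because footnote b of the schedule of activities ties all procedures except tumour imaging to the cycle number, and because treatment is capped at 35 cycles. Exposure, delay and dose-modification data could then mean different things at different sites.

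**Working it through.** No figure in the plan has to be reproduced. The check is a comparison of passages, followed by one bound.

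**Step 1. Meaning of the term.** Sections 6.1.1 and 6.5.1 together give: cycle delay = Day 1 delayed for SAR444245 and for pembrolizumab. Section 6.5.2 (restart of IMPs in the plural) and Table 5 footnote a agree.

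**Step 2. Use of the term in the event tables.**

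| Row | Instruction | Defined term used? | Pembrolizumab addressed? |
|---|---|---|---|
| Table 4, CRS Grade 3 | cycle delay, SAR444245 named | yes | no |
| Table 6, ICANS Grade 2 | delay, SAR444245 named | no | no |
| Table 6, ICANS Grade 3 | delay, SAR444245 named | no | no |
| Table 7, VLS Grade 2 | delay, SAR444245 named | no | no |

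Only the first row conflicts with the definition in its own words. The other three leave open whether the general rule still governs pembrolizumab.

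**Step 3. Does other text settle it?**
- The override clause in 6.5.3 gives way to a specific instruction elsewhere. The tables give none for pembrolizumab, so they can be read as an exception limited to SAR444245 or as silence that leaves the two-drug rule standing.
- The partial-discontinuation text in 6.5.1 lets one drug continue when the other is stopped permanently. It does not cover a temporary delay.
- The most-conservative rule in 6.5.1 is for a participant with several toxicities that attract conflicting advice, not for one event under two rules.
- Section 6.5.4.4 holds both drugs for immune-related events. Master protocol section 6.8.2 puts CRS and ICANS under immune-mediated events but lists irAEs as a separate item beside them, so it is unclear whether that rule reaches CRS or ICANS.
- Table 3 (SAR444245 infusion reactions, Grades 3 and 4) does say that the partner drug can continue. Tables 4, 6 and 7 have no matching line.

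**Step 4. Rows not affected.** For CRS Grade 4, ICANS Grade 4 and VLS Grades 3 and 4, SAR444245 is stopped permanently and the partial-discontinuation text applies.

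**Step 5. Upper bound.** Longest permitted delay: 84 days (6.5.2). Cycle length: 21 days. 84/21 = 4. Counted from the planned Day 1, pembrolizumab would fall on days 0, 21, 42 and 63 under one reading and on none of these under the other; on day 84 both drugs could restart.

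**The case against.** The best defence is that this is silence and not contradiction. No visible text says that pembrolizumab is given while SAR444245 is delayed. The general sections state a two-drug default, the tables are headed for SAR444245 only, and where the sponsor wanted the partner drug continued, Table 3 says so. The Grade 2 row of Table 4 even speaks of resuming the IMP. On this view a careful site holds both drugs. In addition, the tables are recommendations and 6.5.3 leaves the final decision to the investigator.

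Much of this stands for ICANS and VLS, whose rows do not use the defined term; there the fault is an ambiguity. It does not clear CRS Grade 3, where the defined term itself is attached to one drug. Investigator discretion does not tell a site what the default is, and so does not tell a monitor what counts as a deviation.

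The defence is also right on size. The master protocol (8.2) describes cytokine-release manifestations some 12 to 18 hours after the first administration, while the next dose is three weeks later, so many events may have resolved by then. A restart after more than 14 days needs clear benefit and consultation with the sponsor.

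A reader might also infer that Table 5 and Table 6 clash, because Table 5 permanently stops all treatment for Grade 3 neurological toxicity while Table 6 leaves a restart of SAR444245 open after Grade 3 ICANS. The documents do not support this well. ICANS has its own section, its own table and ASTCT grading, Table 5 uses CTCAE grades, and the AESI list names ICANS apart from immune-related events.

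**Conclusion.** The point holds as a wording conflict at CRS Grade 3 and as an unresolved ambiguity at ICANS Grades 2 and 3 and VLS Grade 2. It can lead sites to differ, each within the protocol, on pembrolizumab dosing and cycle counting, but only when the toxicity is still unresolved at the next planned Day 1.

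The difference is at most 4 pembrolizumab administrations per event. The documents do not give the frequency of such delays. For orientation only, master protocol section 4.3 reports Grade 3 CRS in 1 of 20 HAMMER participants on the pembrolizumab combination (5.0%), at 16 µg/kg and graded by CTCAE, not by the ASTCT scale used here.

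A reader might take these events to be the main anticipated toxicities of SAR444245. The master protocol says that of cytokine release, but its section 2.3.1.2 does not anticipate VLS. Nor do the documents show an effect on response: the definition of ORR and the sample size do not depend on this, and tumour imaging follows the calendar from the first dose regardless of delays.

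The conclusion covers Substudy 01 only, because the dose-modification text of the other substudies is not shown. It takes no view on whether pembrolizumab should be given or held.

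**What to change.** Reconcile sections 6.5.1, 6.5.2 and 6.5.3 and footnote a of Table 5 with Tables 4, 6 and 7. Use one definition of cycle delay throughout, and have each delay row (CRS Grade 3, ICANS Grades 2 and 3, VLS Grade 2) state what happens to SAR444245 and what happens to pembrolizumab. If one drug may be given while the other is delayed, use a different term for that and say how the cycle is numbered and counted towards the 35. The clinical choice is the sponsor's.

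Check the other substudies for the same wording. The Substudy 02 change log records a cetuximab column added to its CRS table, so partner-drug instructions in such a table are feasible, and handling there may already differ.

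The cost is a text change at the next amendment, with a matching note to sites. No analysis, sample size or endpoint changes.
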